10.4.9 Efficacy Review

This study will not evaluate efficacy.

10.4.10 Additional Sub-Group Analyses

Primary or secondary endpoints may be analyzed for descriptive purposes by age, race/ethnicity, or any other participant characteristic as described in detail in the SAP.

10.4.11 Multiple Comparison/Multiplicity

For these analyses, the investigators will generally not control for multiple comparisons. Any specific controls for multiple comparisons for the neuroimaging or gene expression data may be considered as part of the SAP.

10.4.12 Tabulation of Individual Response Data

Individual participant data will not be listed.

10.4.13 Exploratory Analyses

See SAP.

CONFIDENTIAL

10.5 Sample Size

The R00 study will recruit up to 32 participants (i.e. 16 participants per group) with analyzable data. Up to 40 participants will be recruited to reach this goal. The projected sample size is sufficient to meet the specific aims of the R00 study and falls within the range of pilot neuroimaging studies.^{53,54} It is unknown what effect sizes for the intervention versus active control will be uncovered for neural markers in this population. However, based on the investigators' finding of large effect sizes for neural markers of cognitive changes in the K99 study, group sample sizes of 16 will achieve 78.1% power to reject the null hypothesis of no effect size when the population effect size is 1 and the significance level (alpha) is 0.05 using a two-sided, two-sample equal variance t-test.

10.6 Measures to Minimize Bias

10.6.1 Enrollment/Randomization/Masking Procedures

After written informed consent at the enrollment visit, participants will complete the baseline assessment (TP0) and be randomly assigned to the MBSR intervention group or HEP active control group in a permuted block design stratified by receipt of chemotherapy (i.e., two strata). It will not be possible to blind study participants or interventionists to group assignment. However, to reduce bias, research staff who conduct participant assessments (TP0, TP1, TP2), including the PI, will be blinded to group assignment (i.e., single blind). Participants will be reminded not to reveal their group assignment to study staff conducting assessments. The study biostatistician will have no direct contact with study participants and will not be blinded to group assignment. The biostatistician will produce and maintain the randomization codes for the permuted blocks. Randomization may only be unmasked by the biostatistician at the completion of analysis of the primary outcome, or for reporting of SAEs or UPs for which it will be essential to provide information to the PI on group assignment.

As described in section 5.7.2, participants who withdraw or are withdrawn from the study may be replaced with additional participants in the next cycle of the intervention with the intent of obtain at least 32 analyzable participants. For this study of preliminary efficacy, which is determining effect sizes, as large an analyzable sample size as possible will refine the estimates of these effect sizes.

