Population	Postmenopausal women with breast cancer in the New York City metropolitan area, aged 18-79
Study Sites	New York University (NYU Langone Health Perlmutter Cancer Center, Bluestone Center for Clinical Research, New York University Center for Brain Imaging)
Number of participants	40 enrolled, with 32 evaluable participants

CONFIDENTIAL

Description of Study Intervention/Procedure	The MBSR group will receive training from a trained instructor during a group-based, 2.5-hour manualized educational activity weekly for eight weeks. Activities include body scans, gentle stretching, yoga, and mindful awareness. Participants will be asked to complete daily 45-minute mindfulness activities on days the group does not meet and a one-day weekend retreat (approximately 7 hours) to reinforce learning. The HEP group, which was developed to serve as an active control for MBSR, will receive manualized health education in physical activity, functional movement, music therapy, and nutrition—without mindfulness instruction—using similar modalities for a matched schedule with the same time requirements.
Reference Therapy	NA
Key Procedures	Functional and structural brain imaging, neuropsychological testing, patient-reported outcomes, and blood draws
Statistical Analysis	See statistical analysis plan (SAP). A formal SAP will be developed for this study in consultation with the study biostatistician. Only a general overview of study statistics is included in this protocol.

CONFIDENTIAL

Schematic of Study Design

Note: Informed consent will be obtained after recruitment before any study procedures begin. Of the 32 subjects recruited with analyzable data, 16 will be randomly assigned to the MBSR group and 16 to the HEP group in a permuted block design, stratified by receipt of chemotherapy (i.e., two strata). Up to 40 participants will be recruited to reach this goal. See Table A (Schedule of Events) for details of specific assessments and specimens collected at each time point, as well as the intervention timeline.

CONFIDENTIAL

1 Key Roles

[name], RN, Assistant Professor
NYU Meyers College of Nursing
[name]
[contact]
[contact]

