7.1 Study Procedures/Evaluations

7.1.1 Study Specific Procedures

After written informed consent, participants will complete the baseline assessment (i.e., TP0) and be randomly assigned to the MBSR or HEP group in a permuted block design stratified by receipt of chemotherapy (i.e., two strata). To reduce bias, research staff who assess participants, as well as the PI, will be blinded to group assignment. At regional community centers, the MBSR group will receive training from a trained instructor during a group-based, approximately 2.5-hour manualized educational activity weekly for eight weeks. Participants will be asked to complete daily 45-minute mindfulness activities on days the group does not meet and a one-day weekend retreat (approximately 7 hours) to reinforce learning. HEP, which was developed to serve as an active control to MBSR, will receive manualized health education, without mindfulness instruction, using similar modalities for a matched schedule with the same time requirements. Participant engagement will be assessed through attendance records, and by percentage of homework completed and mindfulness activities during study participation assessed using REDCap diaries. Assessments will be done at three time points (see Figure – MBSR Study Schema): within three weeks pre-randomization (TP0), within three weeks after completion of the intervention (TP1), and three months (+/- 1.5 weeks) post intervention (TP2). Functional and structural brain imaging will be done at the NYU Center for Brain Imaging at TP0 and TP1. Neuropsychological tests and blood draws will be completed at the Bluestone Center for Clinical Research, Meyers College of Nursing, or New York University Center for Brain Imaging at TP0 and TP2. Neuropsychological tests will not be performed at the post-intervention assessment (i.e., TP1) due to likelihood of practice effects at that interval (i.e., two months). Patient-reported outcomes (see Patient-Reported Outcomes below for detail of these study measures) will be assessed at each time point.

Demographic and Clinical Characteristics. Demographic and clinical characteristics will be collected by patient self-report at TP0 and confirmed, when possible, by medical record review. A list of concomitant medications will be collected from participants at each study visit and confirmed, when possible, by medical record review.

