**Aim 1: Evaluate the preliminary efficacy of MBSR to improve neural markers of cognitive changes during AI therapy.** **fMRI:** Data will be preprocessed using Statistical Parametric Mapping-12 (SPM-12; [www.fil.ion.ucl.ac.uk/spm](http://www.fil.ion.ucl.ac.uk/spm)) to normalize images into standard space so that all brains can be compared. Talairach PickAtlas will be used to define regions of interest (ROIs) for cognitive and emotion processing. Neural activation will be evaluated using the blood-oxygen-level-dependent (BOLD) signal. SPM-12 will extract BOLD activation in these ROIs. Brain activation maps will describe (1) between-group differences in brain activation in ROIs for the MBSR versus active control group pre- and post-intervention and (2) within-group change scores in brain activation for each group pre- to post-intervention. **fcMRI:** BOLD signal time series will be extracted from ROIs of the default mode network. Physiological noise and motion artifact regressors will be removed. Residual time series from each ROI will be filtered between 0.01-0.08 Hz. Analyses will be performed with and without a global signal regressor to assess impact on connectivity. Parameter estimates representing connectivity between neural regions will be extracted. Functional connectivity maps will describe between-group differences in connectivity in ROIs pre- and post-intervention and within-group change scores in connectivity pre- to post-intervention. **dMRI:** Data will be analyzed using ExploreDTI ([www.exploredti.com](http://www.exploredti.com)), FreeSurfer ([surfer.nmr.mgh.harvard.edu](http://surfer.nmr.mgh.harvard.edu)), and the diffusion toolbox of the Functional MRI tool of Brain Software Library ([www.fmrib.ox.ac.uk/fsl](http://www.fmrib.ox.ac.uk/fsl)) to perform quality assurance for images, process them for characterization of the integrity of white matter tracts, and match white matter tracts to structural MRI data. White matter tracts between cortical and subcortical ROIs will be evaluated to describe how white matter integrity is affected. Fractional anisotropy (FA) values for white matter tracts will be extracted. FA maps will describe (1) between-group differences in FA in ROIs for the MBSR versus active control group pre- and post-intervention and (2) within-group change scores in FA pre- to post-intervention.

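### The chemotherapy stratum used in randomisation appears in no planned between-arm analysis; any standard error, test or interval from an unadjusted Aim 1 comparison would be conservative if chemotherapy predicts the outcome

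*Protocol*

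**What the plan says.** Protocol section 10.6.1 allocates participants "in a permuted block design stratified by receipt of chemotherapy (i.e., two strata"). Section 7.1.1 repeats it: "MBSR or HEP group in a permuted block design stratified by receipt of chemotherapy (i.e., two strata"). Section 4.1 says the same, and the note to the study schematic gives the intended evaluable split: "16 will be randomly assigned to the MBSR group and 16 to the HEP group in a permuted block design".

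For fMRI, SAP Aim 1 plans to describe "between-group differences in brain activation in ROIs for the MBSR versus active control group pre- and post-intervention", together with change inside each arm. The fcMRI and dMRI paragraphs are parallel. No model, test or covariate is named for these comparisons, and the SAP text never mentions chemotherapy. Protocol section 10.4.2, on the primary analysis, only refers the reader to the SAP.

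The one between-arm test named in either document is in Protocol section 10.5: "group sample sizes of 16 will achieve 78.1% power" "when the population effect size is 1", where "the significance level (alpha) is 0.05", "using a two-sided, two-sample equal variance t-test". It has no stratum term.

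Two other provisions come near the point. Protocol section 10.4.1 and the SAP's opening paragraph plan a general screen for confounding, with unspecified remedies. Protocol section 10.4.10 allows descriptive subgroup analyses as detailed in the SAP, but the SAP details none. Neither names the stratum.

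**The concern.** Stratified blocks make the arms similar in their share of women who had chemotherapy, so variance between the strata largely drops out of the arm difference. The ordinary pooled t-test does not know this. Its standard error still counts the between-stratum variance, so the calculated uncertainty exceeds the real uncertainty whenever the stratum is prognostic. A model with a stratum term restores the match between design and analysis.

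Effect sizes are the primary output (Protocol section 4.2.1) and will inform the size of a later trial (Protocol section 10.2; SAP, possible problems). If a test or interval accompanies them, it should reflect the design that produced them. Naming the stratum in advance also removes an after-the-fact decision about whether chemotherapy counts as a confounder.

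**Working it through.** **Inputs from the documents.** 16 per arm, effect size 1, two-sided alpha 0.05, unadjusted equal-variance t-test, stated power 78.1% (Protocol 10.5); two chemotherapy strata (10.6.1); 40 enrolled to give 32 evaluable (5.6).

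**Assumed, because the documents do not give them.** R², the share of within-arm outcome variance explained by the stratum, ranged from 0 to 30%; blocks of 4; half the women having had chemotherapy (30% tried as a variant).

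**Step 1: the plan's own figure.** The noncentrality is 1 × √(16/2) = 2.828 with 30 degrees of freedom. The noncentral t distribution gives 78.14%, which reproduces the stated 78.1%.

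**Step 2: the estimate.** In within-arm SD units, the unadjusted t-test works with a standard error of √(2/16) = 0.354. With strata balanced across arms, the true standard error is √((1 − R²) × 2/16) whether or not the stratum is in the model: 0.335 at R² = 10% and 0.296 at 30%. Simulation (12,000 trials per setting) agrees. The SD of the estimate is 0.334 unadjusted and 0.334 adjusted at 10%, and 0.295 and 0.295 at 30%.

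**Step 3: interval and power.** The ratio of 95% interval widths, adjusted to unadjusted, is [t(0.975; 29) / t(0.975; 30)] × √(1 − R²). At R² = 0 it is 1.001; at 10% it is 1.0014 × 0.9487 = 0.950. The unadjusted half-width is 0.722 SD. Adjusted power uses noncentrality 2.828/√(1 − R²) with 29 degrees of freedom.

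| Assumed R² | Width ratio | Adjusted half-width (SD) | Adjusted power | Simulated coverage, unadjusted |
|---|---|---|---|---|
| 0 | 1.001 | 0.723 | 78% | 95.2% |
| 5% | 0.976 | 0.705 | 80% | 95.5% |
| 10% | 0.950 | 0.686 | 82% | 96.1% |
| 20% | 0.896 | 0.647 | 86% | 97.0% |
| 30% | 0.838 | 0.605 | 90% | 98.1% |

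Simulated coverage of the adjusted interval stays between 94.8% and 95.3%. Break-even is at R² of about 0.003.

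The 78.1% baseline slightly flatters the gain, because stratification alone helps the unadjusted test. Its simulated power at R² = 10% is 79.5%, against 82.4% adjusted; at 30% it is 81.6% against 90.5%.

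**Step 4: loss from 40 to 32.** Random loss disturbs the balance. The SD of the estimate, unadjusted and adjusted, becomes 0.338 and 0.335 at R² = 10%, and 0.308 and 0.296 at 30%. The width ratios are 0.950 and 0.835. At R² = 0 the adjusted interval is about 0.5% wider (ratio 1.0047). A 30% chemotherapy share gives nearly the same results.

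**Step 5: what each R² requires.** With equal strata, the mean difference between women with and without chemotherapy is 2√R² within-arm SDs: 0.45 at 5%, 0.63 at 10%, 0.89 at 20% and 1.10 at 30%. The last exceeds the effect size of 1 assumed for the intervention.

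**The case against.** The strongest reply is that little of what the trial plans to report would change. The output is effect sizes, no confidence interval is planned, and both documents disclaim inference to the wider population. With balanced strata and the raw SD as denominator, the effect size barely moves. The SAP does not choose an unadjusted analysis either; it names none, and the t-test appears only in the sample-size section. All of this stands. The point is therefore an omission with a conservative consequence.

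Three stronger readings are tempting, and the documents do not support them.

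- A reader might infer that leaving out the stratum makes the estimated effect noisier. With balanced strata it does not (step 2). After loss from 40 to 32 the gap is small.
- A reader might infer that the trial's confidence intervals will be too wide. None is planned, so this can be said only of an interval or test that someone later takes from the unadjusted comparison.
- A reader might take the imaging studies in Protocol section 2.1 as evidence that chemotherapy is prognostic here. Those studies mix chemotherapy with tamoxifen, and the protocol itself says the contributions cannot be separated. They compare groups years after treatment, whereas the primary endpoint is change across an eight-week programme. A stable difference between the strata cancels from a change score, so R² for change could be close to zero.

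The general screen for confounding could bring chemotherapy into the analysis, but it commits to nothing and would leave the choice until the data are seen.

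**Conclusion.** The point holds as a minor one. Randomisation uses the chemotherapy stratum, and no planned between-arm analysis does. The point estimate is essentially unaffected when the strata are balanced. Any standard error, test or interval from the unadjusted comparison errs on the cautious side, by an amount set by an R² that the documents do not supply. Over the assumed range of 0 to 30%, adjustment changes the interval from about 0.1% wider to about 16% narrower. The upper end needs a chemotherapy effect larger than the intervention effect used for power, so only a few percent may be at stake. Nothing here threatens the validity of the pilot.

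**What to change.** Add a sentence to SAP Aim 1: each MBSR-minus-HEP difference (fMRI, fcMRI and dMRI) is estimated from a linear model with arm and chemotherapy stratum as fixed terms, and the effect size is reported with the 95% confidence interval from that model. State that the effect size is standardised by the raw SD. Dividing by the stratum-adjusted residual SD would inflate it by a factor of 1/√(1 − R²), which is 1.05 at R² = 10% and 1.20 at 30%.

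The cost is one degree of freedom (30 to 29). If chemotherapy predicts nothing, the interval is about 0.1% wider with balanced strata, or about 0.5% wider in the simulated loss from 40 to 32. No new data are needed, because the stratum has to be known at randomisation.

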10.6.2 Evaluation of Success of Blinding

Blinding will be considered successful if, with the exception of SAE and UP reporting, the PI and study staff conducting assessments remain unaware of group assignment until after data collection is complete.

10.6.3 Breaking the Study Blind/Participant Code

Single blinding will be broken before completion of data collection only for reporting of SAEs or UPs for which it will be essential to provide information to the PI on group assignment. For SAEs or UPs that could affect other participants, the entire group will be unblinded so that the PI and study staff can discuss with these participants whether it is safe for them to continue in the study.

While every effort will be made to remind participants not to unblind themselves, it is possible that a participant may unintentionally unblind themselves to study staff conducting assessments or to the PI. If a blind is unintentionally broken, it will be reported to the study biostatistician and discussed by the data and safety monitoring team. Any unintentional unblindings will be reported to the IRB as a deviation from protocol. As this is a pilot study, the participant will be allowed to continue in the study and data will be analyzed.

11 Source Documents and Access to Source Data/Documents

Source data is all information, original records of clinical findings, observations, or other activities in a clinical trial necessary for the reconstruction and evaluation of the trial. Source data are contained in source documents. Examples of these original documents, and data records include: hospital records, clinical and office charts, laboratory notes, memoranda, subjects' diaries or evaluation checklists, pharmacy dispensing records, recorded data from automated instruments, copies or transcriptions certified after verification as being accurate and complete, microfiches, photographic negatives, microfilm

CONFIDENTIAL

or magnetic media, x-rays, subject files, and records kept at the pharmacy, at the laboratories, and at medico-technical departments involved in the clinical trial.

The study case report form (CRF) is the primary data collection instrument for the study. All data requested on the CRF must be recorded. All missing data must be explained. If a space on the CRF is left blank because the procedure was not done or the question was not asked, write "N/D". If the item is not applicable to the individual case, write "N/A". All entries should be printed legibly in black ink. If any entry error has been made, to correct such an error, draw a single straight line through the incorrect entry and enter the correct data above it. All such changes must be initialed and dated. DO NOT ERASE OR WHITE OUT ERRORS. For clarification of illegible or uncertain entries, print the clarification above the item, then initial and date it.

Access to study records will be limited to IRB-approved members of the study team. The investigator will permit study-related monitoring, audits, and inspections by the IRB/EC, the sponsor, government regulatory bodies, and University compliance and quality assurance groups of all study related documents (e.g. source documents, regulatory documents, data collection instruments, study data etc.). The investigator will ensure the capability for inspections of applicable study-related facilities (e.g. Bluestone Center for Clinical Research, Center for Brain Imaging, etc.).

Participation as an investigator in this study implies acceptance of potential inspection by government regulatory authorities and applicable University compliance and quality assurance offices.

12 Quality Assurance and Quality Control

QC procedures will be implemented beginning with the data entry system, and data QC checks that will be run on the database will be generated. Any missing data or data anomalies will be communicated to the site(s) for clarification/resolution.

Following written SOPs in the MOP, the PI will verify that the clinical trial is conducted and data are generated, documented (recorded), and reported in compliance with the protocol, GCP, and the applicable regulatory requirements (e.g., Good Laboratory Practices (GLP)).

The investigational site will provide direct access to all trial related sites, source data/documents, and reports for the purpose of monitoring and auditing by the sponsor, and inspection by local and regulatory authorities.

13 Ethics/Protection of Human Subjects

13.1 Ethical Standard

The investigator will ensure that this study is conducted in full conformity with Regulations for the Protection of Human Subjects of Research codified in 45 CFR Part 46.

13.2 Institutional Review Board

The protocol, informed consent form(s), recruitment materials, and all participant materials will be submitted to the IRB for review and approval. Approval of both the protocol and the consent form must be obtained before any participant is enrolled. Any amendment to the protocol will require review and approval by the IRB before the changes are implemented to the study. All changes to the consent form will be IRB approved; a determination will be made regarding whether previously consented participants need to be re-consented.

13.3 Informed Consent Process

13.3.1 Consent/Assent and Other Informational Documents Provided to Participants

The informed consent form describing in detail the study intervention, study procedures, and risks are given to the participant, and written documentation of informed consent is required prior to starting any

CONFIDENTIAL

study procedures.

13.3.2 Consent Procedures and Documentation

Information will be obtained during screening for the study by study staff or the MRI technologist to determine eligibility. Obtaining this information before written informed consent for the study will save time for potential participants by avoiding unnecessary trips to the study sites at which enrollment will be completed. During screening, study staff will review the purpose, nature, risks, and benefits of the study; determine eligibility; and, if desired, schedule an enrollment appointment at NYU to obtain written informed consent from the candidate. The period of time between screening and enrollment will vary, depending on the availability of the potential participant and recruitment of a sufficient number of potential participants to begin an intervention cycle.

This process will give the potential participant time between screening and enrollment to consider whether she wants to participate in the study. Participants will be reminded when the study is introduced, during screening, and during written informed consent that participation is voluntary and that choosing not to participate in no way affects the quality or quantity of medical or nursing care provided to them. During this time between screening and the enrollment visit, the candidate will have a copy of the consent form. If at any point the candidate prefers not to proceed, the enrollment visit will be canceled. The candidate will be offered time after the in-person review of the consent form during the enrollment visit to think about her potential participation and to ask any questions before choosing to sign the study consent. In addition, subjects are told that they may choose to withdraw from the study at anytime.

Informed consent is a process that is initiated prior to the individual's agreeing to participate in the study and continues throughout the individual's study participation. Extensive discussion of risks and possible benefits of participation will be provided to potential participants. Consent forms will be IRB-approved, and the participant will be asked to read and review the document. The investigator will explain the research study to the participant and answer any questions that may arise. All participants will receive a verbal explanation in terms suited to their comprehension of the purposes, procedures, and potential risks of the study and of their rights as research participants. The participant will sign the informed consent document prior to any procedures being done for the study. The participants may withdraw consent at any time throughout the course of the trial. A copy of the signed informed consent document will be given to the participants for their records. A copy of the signed informed consent document will be stored in the participant's research record. The consent process, including the name of the individual obtaining consent, will be thoroughly documented in the subject's research record. Any alteration to the standard consent process and the justification for such alteration will likewise be documented.

